## 1 BACKGROUND

Over the past 4 decades, allogeneic hematopoietic stem cell transplantation (allo-HSCT) from an HLA-matched donor, either related or unrelated, has been increasingly used to treat patients affected by several malignant or non-malignant disorders. However, only 25% of patients who need or could benefit from an allograft have an HLA-identical sibling and fewer than 60% of remaining patients can be matched with suitable HLA-compatible, unrelated donors (Rocha 2008). In the absence of an HLA-matched donor, alternative donor/sources of hematopoietic stem cells such as HLA-haploidentical relatives are being increasingly used. While mature donor T cells present in the graft facilitate T-cell reconstitution, in the context of increased immune genetic disparity between patient and donor, the T cells are also responsible for the occurrence of graft-versus-host disease (GVHD), a severe, sometimes fatal, immune complication, which also impairs patient's immune reconstitution.

Strategies to prevent GVHD after HLA-haploidentical allo-HSCT based on either pharmacological immunosuppression or T-cell depletion of the graft have been developed. In particular, the physical elimination of T cells from the graft has been shown to be highly effective to prevent both acute and chronic GVHD (cGVHD). However, with T-cell depletion of the graft, the patient cannot benefit from the adoptive transfer of donor-derived memory T lymphocytes, which are mainly responsible for protection from severe infections during the state of profound immune deficiency that usually lasts for at least 4-6 months after transplantation. Overall, HLA-haploidentical allo-HSCT is associated with a higher incidence of graft rejection, and both viral and fungal infections, resulting in high transplantation-related mortality (TRM).

US and European gene therapy guidelines require monitoring delayed adverse events in patients who are exposed to gene therapy products for a period of 5-15 years depending on the nature of the product. A potential, but rare, risk of gene therapy using retroviral vectors is the generation of a replication competent retrovirus. This long term follow-up observation period provides a chance to mitigate risks associated with the gene therapy.

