## 2 SYNOPSIS

Study Identifier(s)	BP-404 EudraCT #2016-003226-16
Aim of the Study	This is a Phase I/II study to evaluate the long-term safety of the infusion of BPX-501 gene-modified T cells after mismatched, T cell-depleted allogeneic transplantation and evaluate disease free survival at 1 and 2 years post-transplant
Study Design	
Open label, multi-centre, non-randomized, non-controlled long-term safety evaluation
 
Follow-up of all patients enrolled on BP-004 and treated with BPX-501 who are beyond Day 180 and have completed or discontinued the parent study.

Study Population	The patient population is identical to BP-004 as it is the long-term follow-up of those patients. Estimated enrolment up to 175 BP-004 patients.
Main Inclusion Criteria	
 
1. Signed written informed consent by the patient or the patient's guardian for children who are minors
 
2. Enrolled on BP-004 protocol, received BPX-501 infusion, completed or discontinued from the study, and are beyond Day 180.
 

Main Exclusion Criteria	
 
1. Lack of parents'/guardian's informed consent for children who are minors
 
2. Withdrawal from BP-004 study prior to BPX-501 infusion.
 

Dosage, Treatment Regimen, Route of Administration	
No BPX-501 infusions will be administered under this protocol.
 
Rimiducid to be given at 0.4 mg/kg weight (intravenous infusion) only in the setting of uncontrolled GVHD.

Locations (e.g. regions)	Italy, Saudi Arabia.
Primary Endpoint(s) with Time Point(s) of Assessment	Overall Survival and incidence of Disease-Free Survival in both malignant and non-malignant patients at 1 year and 2 years post-transplant. Relapse-Free Survival in malignant patients at 1 year and 2 years post-transplant.
Main Secondary Endpoint(s) with Time(s) of Assessment	Long-term safety for a total of 15 years from BPX-501 administration

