3.2. Study Endpoint(s)

Endpoints will be further defined in subsequent sections. Unless otherwise specified, time-to-event endpoints will be calculated from the date of HSC infusion. If a patient received more than one HSCT, the time of the last HSC infusion immediately preceding infusion with BPX-501 will be the transplant date.

Primary Endpoint:

Event-Free Survival (EFS) at 180 days. Events are defined as the first occurrence of either transplant-related mortality (TRM) for non-malignant patients or non-relapse mortality (NRM) for malignant patients, severe GvHD (Grade 2-4 acute organ GvHD or extensive/moderate-severe chronic GVHD), and life-threatening infections (Grade 4).

NB: In the BPX-501 protocols, the terminology 'extensive' chronic GvHD was used. For the purposes of the primary analysis and for the rest of this SAP, extensive chronic GvHD will be defined as moderate or severe chronic GvHD. 'Overall' chronic GvHD or chronic GvHD without a qualifier will be interpreted as mild, moderate or severe chronic GvHD.

The following secondary endpoints are in the BP-004 protocols, although additional endpoints and analyses are described below in subsequent sections of this document.

Secondary Endpoints:

- (i) Transplant-Related Mortality (TRM) in patients with non-malignant diagnoses or Non-Relapse Mortality (NRM) in patients with malignant diagnoses at 100 and 180 days
- (ii) Cumulative incidence and severity of acute GvHD (any Grade 2-4 or Grade 3-4) as well as overall and moderate-severe chronic GvHD at 180 days.
- (iii) Time to resolution of acute GvHD after administration of rimiducid
- (iv) Immune reconstitution as determined by T cell subsets up through 180 days
 - a. Absolute CD3 count
 - b. Absolute CD4 count

- c. Absolute CD8 count
- (v) Time-to-immune reconstitution defined by CD3 count > 500 cells/uL; CD4 count > 200 cells/uL; CD8 count of 200 cells/uL
- (vi) Disease-Free/chronic GvHD Survival (DFGS) defined as the first of either disease recurrence, death from any cause, or chronic GVHD
- (vii) Disease status within the following disease indications at 180 days:
 - a. Primary immune disorders as determined by CD3 T cell count ≥ 500 cells/uL and normal levels of IgA and IgM
 - b. Haemoglobinopathies as determined by incidence of RBC transfusion independence for 8 consecutive weeks and untransfused haemoglobin of ≥ 8.5 g/dL

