Cumulative incidence of acute leukemia relapse will be estimated from time of transplant using a Nelson-Aalen cumulative incidence function and treating death prior to relapse as a competing risk. Cumulative incidence plots with descriptive summary statistics including incidence and 95% confidence intervals will be presented.

(ii) Time to Neutrophil Engraftment

Events for neutrophil engraftment is defined as the first of three consecutive measurements of an ANC $\geq 500/\mu\text{L}$ following the conditioning regimen induced nadir, starting from Day 0 (day of transplant). A patient that does not achieve the count of ANC $\geq 500/\mu\text{L}$ will be censored at the last assessment date.

Time to neutrophil engraftment will be estimated using a Nelson-Aalen cumulative incidence function. Death will be considered a competing event. Cumulative incidence plots with descriptive summary statistics including median engraftment time and 95% confidence intervals will be presented.

(iii) Time to Platelet Engraftment

Events for platelet engraftment is defined as the first of three consecutive measurements of platelet count $\geq 20,000/\mu\text{L}$ without platelet transfusion support for seven days. A patient that does not achieve the threshold platelet count of $\geq 20,000/\mu\text{L}$ as required will be censored at the last assessment date.

Time to platelet engraftment will be estimated using a Nelson-Aalen cumulative incidence function. Death will be considered a competing event. Cumulative incidence plots with descriptive summary statistics including median engraftment time and 95% confidence intervals will be presented.

(iv) Analysis of Primary and Secondary Graft Failure

Primary graft failure is defined as failure to achieve an absolute ANC ≥ 500 cells/ μ L by Day 30. The proportion of patients experiencing primary graft failure in the first 30 days will be summarized and reported with a 95% confidence interval.

Secondary graft failure is defined as initial neutrophil engraftment followed by a subsequent decline in neutrophil counts to < 500 cells/ μ L which is unresponsive to growth factor therapy. Sustained neutropenia, i.e., neutrophil counts to < 500 cells/ μ L, observed for greater than 30 days from the administration of growth factors will be summarized.

(v) Infectious Complications

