6.7. Additional Exploratory Analyses

Other exploratory subgroup analyses to characterize safety and efficacy activities for BPX-501 may be conducted. These additional exploratory analyses will be decided at the time of final data analysis.

Sparse PK sampling collected from patients that receive rimiducid will be used to determine the concentration time profile of rimiducid in plasma and summarized as described above. Rimiducid plasma concentration data collected from these subjects will be used as part of a population PK modeling and meta-analysis that will be presented in a separate document. Additional PK assessments may be performed as deemed appropriate.

In addition to the pharmacodynamic and translational analyses specified above, further exploratory analyses are planned and will also be presented in separate documents. These analyses include, among others, analysis of CD45RO/CD45RA/CD62L/CCR7, T cell diversity, and thymic function.

The following additional efficacy analyses were not specified in the protocol, but are being proposed in order to assess longer-term outcomes beyond 180 days and to harmonize with other

study protocols investigating the use of BPX-501. The analyses will be conducted in the ITT population, and, possibly, in the PP population as well.

- (i) Transplant-Related Mortality and Non-Relapse Mortality, defined earlier, at 1 year and 2 years from the time of HSCT. TRM and NRM at those time points will be estimated using a Nelson-Aalen cumulative incidence function.
- (ii) Overall Survival, defined as the time from HSCT to death due to any cause, at 180 days, 1 year and 2 years. Overall survival will be analyzed in all patients as well as stratified by disease subtype (malignant and non-malignant). Overall survival at those time points will be estimated using a Kaplan-Meier survival function.
- (iii) Disease-Free Survival, defined as the time from HSCT to disease recurrence or death, whichever occurs first, in subjects with non-malignant disease. DFS will be estimated at 180 days, 1 year and 2 years using a Kaplan-Meier survival function.
- (iv) Relapse-Free Survival, defined as the time from HSCT to disease relapse or death, whichever occurs first, in subjects with malignant disease. RFS will be estimated at 180 days, 1 year and 2 years using a Kaplan-Meier survival function.

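### DFS in non-malignant patients counts only recurrence or death, so a second transplant after BPX-501 may leave a child event-free

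*SAP*

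**What the plan says.** **BP-404 protocol.** The Synopsis lists as primary "Overall Survival and incidence of Disease-Free Survival in both malignant and non-malignant patients at 1 year and 2 years post-transplant", together with relapse-free survival in malignant patients. Sections 5.1, 7.2 and 9.3 repeat DFS at these time points. None defines it. Section 10.4.5 has subsections for overall survival, graft failure, chronic GVHD, relapse, transplant-related mortality and immune reconstitution, but none for DFS. Section 10.4.2 says only that it will be summarised descriptively.

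**SAP.** It is written for BP-004, but its Introduction allows analyses after Day 180 to draw on BP-404 data and lets its methods override the protocols. Section 6.7 presents the longer-term endpoints in these terms: "The following additional efficacy analyses were not specified in the protocol, but are being proposed in order to assess longer-term outcomes beyond 180 days". Item (iii) gives "Disease-Free Survival, defined as the time from HSCT to disease recurrence or death, whichever occurs first, in subjects with non-malignant disease", and adds that "DFS will be estimated at 180 days, 1 year and 2 years using a Kaplan-Meier survival function". Tables 14.2.13.2 and 14.2.13.3 are planned for it.

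**Graft failure.** SAP 6.4.3(iv) treats it as its own outcome. Primary failure is not reaching an ANC of 500 by Day 30. For secondary failure, "Secondary graft failure is defined as initial neutrophil engraftment followed by a subsequent decline in neutrophil counts" below 500 that does not respond to growth factor. Both go to Table 14.2.11 and Listing 16.2.6.8.

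**More than one transplant.** SAP 3.2 says "the time of the last HSC infusion immediately preceding infusion with BPX-501 will be the transplant date", and 6.2.3 applies the same rule to study Day 1.

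**The concern.** The documents treat loss of the graft as a real hazard of this procedure. The protocol Background says "HLA-haploidentical allo-HSCT is associated with a higher incidence of graft rejection", and the SAP Introduction gives help with engraftment as one of the purposes of BPX-501. A reader will take 1- and 2-year DFS as the share of children whose disease stays controlled after the studied transplant plus BPX-501. If a child loses that graft and is kept disease-free by another one, an endpoint that ignores both the loss and the second transplant may count the child as a success of the first. The failure left out is one the product is meant to help prevent, and the figure affected belongs to a primary endpoint.

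**Working it through.** **1. Event lists side by side**

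| Outcome | Place in SAP | Events | Graft failure or second HSCT counted? |
|---|---|---|---|
| DFS, non-malignant | 6.7(iii) | recurrence, death | No |
| Event-free survival | 6.4.1 | TRM/NRM, severe GvHD, Grade 4 infection | No |
| Disease-free/chronic-GvHD-free survival | 6.4.2(vi) | chronic GvHD, relapse or recurrence, death | No |
| Graft failure | 6.4.3(iv) | neutrophil criteria | Own outcome; feeds no survival endpoint |

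**2. Second transplant.** The rule in 3.2 and 6.2.3 only fixes time zero, as the last HSCT before BPX-501. The dropout rule in 6.2.2 censors at study withdrawal. Nothing makes an HSCT given after BPX-501 an event or a censoring point.

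**3. One case traced.** A child with a haemoglobinopathy engrafts, receives BPX-501, has secondary graft failure at Month 4, and is re-transplanted before any recurrence is recorded. The child is alive at 2 years. Time zero stays at the first transplant. No recurrence and no death are recorded, so the child is event-free at 1 and 2 years. Had the graft loss been entered as recurrence, the same child would be an event at Month 4. Neither document says which entry is right, because recurrence is not defined for non-malignant disease. The disease-status criteria in 6.4.2(vii) describe reaching targets by Day 180, not losing them.

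**4. Direction.** With complete follow-up, adding events to a composite can only lower the event-free share or leave it unchanged. DFS on the present wording is therefore too high or unaffected.

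**5. Size.** The plan has no DFS figure to reproduce. It gives no expected DFS, no graft-failure rate and no number of non-malignant patients. BP-404 takes its sample size from BP-004, and the SAP's power statement concerns event-free survival at Day 180. The following is an illustration on assumed inputs:

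- DFS on the present definition: 90% (assumed).
- g: share of non-malignant children alive after graft loss with no other DFS event, 2%, 5% or 10% (assumed).
- s: share of those already coded as recurrence, 0, 0.5 or 1 (assumed).
- Revised DFS = 90% − g × (1 − s).

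| g | s = 0 | s = 0.5 | s = 1 |
|---|---|---|---|
| 2% | 90 − 2 = 88% | 90 − 1 = 89% | 90% |
| 5% | 90 − 5 = 85% | 90 − 2.5 = 87.5% | 90% |
| 10% | 90 − 10 = 80% | 90 − 5 = 85% | 90% |

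With an assumed 80 non-malignant children and s = 0, the uncounted events are 80 × 0.02 = 1.6, 80 × 0.05 = 4 and 80 × 0.10 = 8.

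**The case against.** The strongest reply has four parts.

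- **Scoring is not settled.** A site may code graft loss with return of the disorder as recurrence. This stands: a reader might infer that such a child is certainly scored as disease-free, and the documents do not support that. It does not rescue the endpoint, because the result then depends on each site's reading.
- **The definition is exploratory and belongs to BP-004.** This also stands. BP-404's DFS covers malignant and non-malignant patients, whereas 6.7(iii) covers only the latter. One cannot say that BP-404 itself adopted the recurrence-or-death rule. It left the endpoint undefined, and this SAP, which may use BP-404 data, holds the only rule written down.
- **Survival without disease regardless of rescue transplant is a coherent question, and graft failure is reported separately.** Both are true, so graft failures are not hidden. But neither document says that this is the question intended. The planned graft-failure summaries also give no 1- or 2-year estimate, and no split by disease group is required, so a reader could not correct the DFS curve from them.
- **The Day-30 neutrophil rule is a poor DFS event.** This stands. A child who first reaches an ANC of 500 after Day 30 would become a permanent failure despite later engrafting. The fix avoids this.

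A reader might also take graft failure to be the leading failure in non-malignant disease. The SAP Introduction's sentence on graft failure concerns paediatric AML, and the protocol Background speaks of haploidentical transplant in general. Neither ranks failures for non-malignant disease.

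**Conclusion.** The point holds as a defect of wording with a known direction. On the only written definition, a child re-transplanted after BPX-501 without recorded recurrence would remain event-free, and DFS may credit the rescue graft to the studied treatment.

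Any bias is upward or zero. It is zero if no such case occurs or if every one is coded as recurrence. The size cannot be derived from the documents. In the illustration it runs from 0 to 10 percentage points, all on assumed inputs. Another tempting calculation multiplies an assumed 2–10% re-transplanted by an assumed 60–90% alive without recurrence at 2 years, giving 0.02 × 0.60 = 1.2 to 0.10 × 0.90 = 9 points. That should not be read as an estimate either: both inputs are assumed, and its lower end wrongly rules out zero.

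The change should be made because the endpoint is primary in BP-404 and the correction is cheap. It does not touch the SAP's non-inferiority power, which rests on Day-180 event-free survival.

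**What to change.** In SAP 6.7(iii), define non-malignant DFS as time from HSCT to the first of:

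- disease recurrence;
- a second HSCT after BPX-501;
- secondary graft failure as defined in 6.4.3(iv);
- death.

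In the same section:

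- State that loss of the graft with return of the underlying disorder counts as recurrence.
- State that not reaching an ANC of 500 by Day 30 is not an event by itself when the child later engrafts without a second HSCT.
- Report DFS counting recurrence or death only alongside, as a sensitivity analysis.

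In 6.4.2(vi), add the same events for non-malignant patients. That endpoint already counts chronic GvHD as well.

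**Cost.** SAP wording, one extra output and a possibly lower DFS figure. Graft failures (Listing 16.2.6.8) and HSCT infusions (Listing 16.2.5.1) are already planned. The sponsor should check that BP-404 records transplants given after BPX-501, since neither its schedule of events nor its list of treatments to be collected names them.

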7. ATTACHMENTS

7.1. Table of Contents for Data Display Specifications

Any changes to format, layout, titles, numbering, or any other minor deviation will not necessitate a revision to the SAP nor will it be considered a deviation from planned analyses. Only true differences in the analysis methods or data handling will necessitate such documentation.

Minor modifications may be necessary to the planned design of tables, listings and figures to accommodate data collected during the actual study conduct. Any major deviations from the final approved SAP, e.g., change in the population used, change from statistical methods or assumptions listed, transformation of data type, exclusion of planned analysis, or additional unplanned analyses will be documented, with justification, in the CSR.

7.1.1. Planned Data Outputs

The following outputs are intended to be produced for the study (NB: Numbering is indicative only and may be updated based on CSR requirements):

Tables:

- 14.1.1.1 Number of Subjects by Analysis Population and Disposition
- 14.1.1.2 Summary of Study Analysis Populations
- 14.1.1.3 Major Protocol Deviations and Violations
- 14.1.2.1 Subject Demographics at Baseline
- 14.1.2.2 Baseline Primary Disease Type, Conditioning and Treatment History
- 14.1.2.3 Donor Demographics, Relationships and HLA Typing
- 14.1.4.1 Prior Medications Use
- 14.1.4.2 Concomitant Medications Use
- 14.1.5 Study Treatment Exposure
- 14.2.1.1 Kaplan-Meier Parameter Estimates of Event-Free Survival
- 14.2.1.2 Kaplan-Meier Parameter Estimates of Event-Free Survival: Sensitivity Analysis for Any Grade 2-4 Acute GvHD
- 14.2.1.3 Kaplan-Meier Parameter Estimates of Event-Free Survival: Sensitivity Analysis on Dosing Window
- 14.2.1.4 Kaplan-Meier Parameter Estimates of Event-Free Survival: Sensitivity Analysis for Death from Any Cause
- 14.2.1.5 Kaplan-Meier Parameter Estimates of Event-Free Survival: Sensitivity Analysis for Dose in Subjects with Malignant Disease
- 14.2.2 Cumulative Incidence Function Parameters Time to Transplant-Related or Non-Relapse Mortality
- 14.2.3.1 Cumulative Incidence Function Parameters Time to Acute GvHD Grades 2-4

- 14.2.3.1.1 Cumulative Incidence Function Parameters Time to Acute GvHD: Grade 2 Organ, Grades 3-4
- 14.2.3.2 Cumulative Incidence Function Parameters Time to Acute GvHD Grades 3-4
- 14.2.3.3 Cumulative Incidence Function Parameters Time to Severe Chronic GvHD
- 14.2.3.3.1 Cumulative Incidence Function Parameters Time to Moderate or Severe Chronic GvHD
- 14.2.3.4 Cumulative Incidence Function Parameters Time to Chronic GvHD Mild-Severe

- 14.2.4.1 Kaplan-Meier Parameter Estimates of Time to Resolution of Acute GvHD After Rimiducid Administration
- 14.2.4.2 Kaplan-Meier Parameter Estimates of Time to Resolution of Chronic GvHD After Rimiducid Administration
- 14.2.4.3 Kaplan-Meier Parameter Estimates of Time to Resolution of GvHD (Acute or Chronic) After Rimiducid Administration
- 14.2.4.4 Best Overall Clinical Response to Rimiducid in Subjects with Acute or Chronic GvHD
- 14.2.4.5 GvHD Types and Grades
- 14.2.5 Immune Reconstitution
- 14.2.6 Cumulative Incidence Function Parameters of Time to Immune Reconstitution of CD3, CD4, and CD8 T-cell Counts
- 14.2.7 Kaplan-Meier Parameter Estimates of Time to Disease-Free/Chronic-GvHD-Free Survival

- 14.2.8.1-3 Cumulative Incidence Function Parameters of Time to Recovery of Primary Immune Disorders as Determined by CD3 T Cell Count >500 cells/uL, and Normal Levels of IgA and IgM

- 14.2.8.2 Cumulative Incidence Function Parameter Estimates of Time to Recovery of Haemoglobinopathies as Determined by Incidence of RBC Transfusion Independence and Haemoglobin of >8.5 g/dL
- 14.2.8.3-3 Cumulative Incidence Function Parameter Estimates of Time to Recovery of Fanconi Anemia as Determined by RBC > 3,000,000 cells/uL, Neutrophil Count > 1500 cells/uL, and Platelet Count >150,000
- 14.2.8.4 Kaplan-Meier Parameter Estimates of Relapse-Free Survival in Subjects with Leukemia
- 14.2.8.5 Cumulative Incidence of Relapse in Subjects with Acute Leukemia
- 14.2.9 Cumulative Incidence Function Parameter Estimates of Time to Neutrophil Engraftment
- 14.2.10 Cumulative Incidence Function Parameter Estimates of Time to Platelet Engraftment
- 14.2.11 Graft Failures

- 14.2.12.1 Time to Any Grade Infection
- 14.2.12.2 Time to Grade 3 or Higher Infection
- 14.2.13.1 Kaplan-Meier Parameter Estimates of Overall Survival
- 14.2.13.2 Kaplan-Meier Parameter Estimates of Disease-Free Survival in Subjects with Non-Malignant Disease
- 14.2.13.3 Sensitivity Analysis: Kaplan-Meier Parameter Estimates of Disease-Free Survival, by Dosing Window
- 14.2.13.4 Kaplan-Meier Parameter Estimates of Relapse-Free Survival in Subjects with Malignant Disease
- 14.2.13.5 Sensitivity Analysis: Kaplan-Meier Parameter Estimates of Relapse-Free Survival, by Dosing Window in Subjects Dosed at 1×10^6 Cells/kg
- 14.2.13.6 Sensitivity Analysis: Kaplan-Meier Parameter Estimates of Relapse-Free Survival, by Dosing Window in Subjects Dosed at 1×10^6 Cells/kg or Above
- 14.3.1.1 Treatment-Emergent Adverse Events Summary
- 14.3.1.2 Treatment-Emergent Adverse Events Regardless of Relationship to Study Treatment by System Organ Class, Preferred Term, and Dose of BPX-501
- 14.3.1.3 Treatment-Emergent Adverse Events Related to Occurring After AP1903 Administration, by System Organ Class, Preferred Term, and Dose of BPX-501
- 14.3.1.4.1 Treatment-Emergent Adverse Events Regardless of Relationship to Study Treatment, by System Organ Class, Preferred Term, and Maximum Severity
- 14.3.1.4.2 Treatment-Emergent Adverse Events Occurring After AP1903 Administration, by System Organ Class, Preferred Term, and Maximum Severity
- 14.3.1.5.1 Treatment-Emergent Infection Adverse Events Regardless of Relationship to Study Treatment, by Preferred Term and Maximum Severity
- 14.3.1.5.2 Treatment-Emergent Infection Adverse Events Regardless of Relationship to Study Treatment, by Preferred Term and Maximum Severity
- 14.3.1.5.3 Treatment-Emergent Adverse Events Grades 3-5 Regardless of Relationship to Study Treatment, by System Organ Class, Preferred Term and Maximum Severity
- 14.3.1.5.4 Treatment-Emergent Neurotoxicity Adverse Events Regardless of Relationship to Study Treatment, by Preferred Term and Dose of BPX-501
- 14.3.2.1 Serious Treatment-Emergent Adverse Events Regardless of Relationship to Study Treatment by System Organ Class, Preferred Term, and Dose of BPX-501
- 14.3.2.2 Serious Treatment-Emergent Adverse Events Occurring After AP1903 Administration, by System Organ Class, Preferred Term, and Dose of BPX-501
- 14.3.2.4 Serious Treatment-Emergent Adverse Events Regardless of Relationship to Study Treatment, by System Organ Class, Preferred Term, and Maximum Severity
- 14.3.2.6 Serious Treatment-Emergent Adverse Events Occurring After AP1903 Administration by System Organ Class, Preferred Term, and Maximum Severity

- 14.3.2.7.1 Treatment-Emergent Adverse Events by Malignant or Non-Malignant Disease Type
- 14.3.2.7.2 Serious Treatment-Emergent Adverse Events by Malignant or Non-Malignant Disease Type
- 14.3.2.7.3 Grade 3-5 Treatment-Emergent Adverse Events by Malignant or Non-Malignant Disease Type
- 14.3.2.8 Summary of Deaths
- 14.3.2.9 Summary of Hospitalizations
- 14.3.4.1.1 Infection Adverse Events Requiring Antiviral, Antibacterial or Antifungal Concomitant Medication Use Within 7 Days
- 14.3.4.1.2 Hematology Results Observed by Visit and Change from Baseline
- 14.3.4.1.2 Hematology Results Shift from Baseline
- 14.3.4.2.1 Chemistry Results Observed by Visit and Change from Baseline
- 14.3.4.2.2 Chemistry Results Shift from Baseline
- 14.3.4.3 Vital Signs Observed by Visit and Change from Baseline

Figures:

- 14.2.1.1 Kaplan-Meier Plot of Event-Free Survival
- 14.2.1.2 Kaplan-Meier Parameter Estimates of Event-Free Survival: Sensitivity Analysis for Any Grade 2-4 Acute GvHD
- 14.2.1.3 Kaplan-Meier Parameter Estimates of Event-Free Survival: Sensitivity Analysis on Dosing Window Subgroups
- 14.2.1.4 Kaplan-Meier Parameter Estimates of Event-Free Survival: Sensitivity Analysis for Death from Any Cause
- 14.2.1.5 Kaplan-Meier Parameter Estimates of Event-Free Survival: Sensitivity Analysis for Dose in Subjects with Malignant Disease
- 14.2.2 Cumulative Incidence Function Plot of Time to Transplant-Related or Non-Relapse Mortality
- 14.2.3.1.1 Cumulative Incidence Function Parameters Time to Acute GvHD: Grade 2 Organ, Grades 3-4
- 14.2.3.1 Cumulative Incidence Function Plot of Time to Acute GvHD Grades 2-4
- 14.2.3.2 Cumulative Incidence Function Plot of Time to Acute GvHD Grades 3-4
- 14.2.3.3.1 Cumulative Incidence Function Parameters Time to Moderate or Severe Chronic GvHD
- 14.2.3.3.2 Cumulative Incidence Function Plot of Time to Severe Chronic GvHD
- 14.2.3.3.3 Cumulative Incidence Function Plot of Time to Overall (Mild-to-Severe) Chronic GvHD
- 14.2.4.1 Kaplan-Meier Plot of Time to Resolution of Acute GvHD After Rimiducid Administration

- 14.2.4.2 Kaplan-Meier Plot of Time to Resolution of Chronic GvHD After Rimiducid Administration
- 14.2.4.3 Kaplan-Meier Plot of Time to Resolution of GvHD (Acute or Chronic) After Rimiducid Administration
- 14.2.5.1 Plot of of CD3 T Cell Counts Across Study Visit Time Points to 180 Days
- 14.2.5.2 Plot of of CD4 T Cell Counts Across Study Visit Time Points to 180 Days
- 14.2.5.3 Plot of of CD8 T Cell Counts Across Study Visit Time Points to 180 Days
- 14.2.5.4.1 Plot of CD3+CD19+ T Cell Counts Across Study Visit Time Points to 180 Days
- 14.2.5.4.2 Plot of the Proportion of CD3+CD19+ T Cells Across Study Visit Time Points to 180 Days
- 14.2.5.4.3 Plot of CD3+CD19+ T Cell Counts Before and After Treatment with Rimiducid
- 14.2.5.4.4 Plot of the Proportion of CD3+CD19+ T Cells Before and After Treatment with Rimiducid
- 14.2.5.5 Plot of B Cell Counts Across Study Visit Time Points to 180 Days
- 14.2.5.6 Plot of NK Cell Counts Across Study Visit Time Points to 180 Days
- 14.2.5.7 Plot of Immunoglobulin A Levels Across Study Visit Time Points to 180 Days
- 14.2.5.8 Plot of Immunoglobulin M Levels Across Study Visit Time Points to 180 Days
- 14.2.5.9 Plot of Immunoglobulin G Levels Across Study Visit Time Points to 180 Days
- 14.2.6.1 Cumulative Incidence Function Plot of Time to Immune Reconstitution of CD3 T-cell Count
- 14.2.6.2 Cumulative Incidence Plot of Time to Immune Reconstitution of CD4 T-cell Count
- 14.2.6.3 Cumulative Incidence Plot of Time to Immune Reconstitution of CD8 T-cell Count
- 14.2.7 Kaplan-Meier Plot of Time to Disease-Free/Chronic-GvHD-Free Survival
- 14.2.8.1.1 Cumulative Incidence Function Parameters of Time to Recovery of Primary Immune Disorders as Determined by CD3 T Cell Count >500 cells/uL, and Lower Normal Levels of IgA and IgM
- 14.2.8.1.2 Cumulative Incidence Function Parameters of Time to Recovery of Primary Immune Disorders as Determined by Normal Range IgA
- 14.2.8.1.3 Cumulative Incidence Function Parameters of Time to Recovery of Primary Immune Disorders as Determined by Normal Range IgM
- 14.2.8.2 Cumulative Incidence Function Parameter Estimates of Time to Recovery of Haemoglobinopathies as Determined by Incidence of RBC Transfusion Independence and Haemoglobin of >8.5 g/dL
- 14.2.8.3.1 Cumulative Incidence Function Parameter Estimates of Time to Recovery of Fanconi Anemia as Determined by RBC > 3,000,000 cells/uL, RBC Transfusion Independence and Haemoglobin of >8.5 g/dL
- 14.2.8.3.2 Cumulative Incidence Function Parameter Estimates of Time to Recovery of Fanconi Anemia as Determined by Neutrophil Count > 1500 cells/uL

- 14.2.8.3.3 Cumulative Incidence Function Parameter Estimates of Time to Recovery of Fanconi Anemia as Determined by Platelet Count > 150,000 cells/uL
- 14.2.8.4 Kaplan-Meier Plot of Relapse-Free Survival in Subjects with Leukemia
- 14.2.8.5 Cumulative Incidence of Relapse in Subjects with Acute Leukemia
- 14.2.9 Cumulative Incidence Plot of Time to Neutrophil Engraftment
- 14.2.10 Cumulative Incidence Plot of Time to Platelet Engraftment
- 14.2.12.1 Time to Any Grade Infection
- 14.2.12.2 Time to Grade 3 or Higher Infection
- 14.2.13.1 Kaplan-Meier Plot of Overall Survival
- 14.2.13.2 Kaplan-Meier Plot of Disease-Free Survival in Subjects with Non-Malignant Disease
- 14.2.13.3 Sensitivity Analysis: Kaplan-Meier Parameter Estimates of Disease-Free Survival, by Dosing Window
- 14.2.13.4 Kaplan-Meier Plot of Relapse-Free Survival in Subjects with Malignant Disease
- 14.2.13.5 Sensitivity Analysis: Kaplan-Meier Parameter Estimates of Relapse-Free Survival, by Dosing Window in Subjects Dosed at 1×10^6 Cells/kg
- 14.2.13.6 Sensitivity Analysis: Kaplan-Meier Parameter Estimates of Relapse-Free Survival, in Subjects Dosed at 1×10^6 Cells/kg or Above
- 14.2.13.7 Sensitivity Analysis: Kaplan-Meier Parameter Estimates of Relapse-Free Survival, by Dosing Window in Subjects Dosed at 1×10^6 Cells/kg or Above

Listings:

- 16.2.1.1 Subjects Screening, Enrollment and Eligibility Criteria
- 16.2.1.2 Donor Screening and Eligibility Criteria
- 16.2.1.3 On-Study Duration
- 16.2.2 Protocol Deviations and Violations
- 16.2.3.1 Analysis Populations
- 16.2.3.2 Subjects Excluded from Efficacy Analysis Populations and Reasons for Exclusion
- 16.2.3.3 Subjects Enrolled into the Study Without Transplantation
- 16.2.3.4 Subjects Receiving Transplantation But No Infusion of BPX-501
- 16.2.4.1 Subject Demographics
- 16.2.4.2 Donor Demographics
- 16.2.4.3 Medical History
- 16.2.4.4 Primary Disease Diagnosis and Treatment History
- 16.2.4.5 Subject/Donor Relation and HLA Typing
- 16.2.4.6 Subject Infectious Disease Testing
- 16.2.4.7 Donor T-cell Leukapheresis and Stem Cell Apheresis
- 16.2.4.8 Medications/Procedures/Treatments Within 30 Days Prior to Conditioning

- 16.2.4.9.1 Concomitant Medications Use
- 16.2.4.9.2 Concomitant Medications Administered for the Treatment of Graft-versus-Host Disease
- 16.2.4.9.3 Concomitant Medications Administered for the Treatment of Graft-versus-Host Disease in Subjects Subsequently Treated with Rimiducid
- 16.2.4.10 Blood Product Transfusion
- 16.2.5.1 HSCT Infusion
- 16.2.5.2 BPX-501 Infusion
- 16.2.5.3 Rimiducid (AP1903) Administration
- 16.2.6.1.1 Listing of Event-Free Survival
- 16.2.6.1.2 Listing of Follow-On Event-Free Survival Events Among Patients with Prior EFS-Qualifying Events
- 16.2.6.1.3 Listing of Overall Survival, Disease-Free Survival, Relapse-Free Survival
- 16.2.6.1.4 Listing of Transplant-Related Mortality or Non-Relapse Mortality
- 16.2.6.2.1 GvHD Types, Severity Score and Time of Occurrence
- 16.2.6.2.2 Listing of Disease-Free/Chronic-GvHD-Free Survival
- 16.2.6.3 Patients Experienced GvHD and Treatment Outcome with Rimiducid (AP1903)
- 16.2.6.4 Mortality and Time of Occurrence
- 12.2.6.5.1 Immune Reconstitution as Determined by Different T-cell Types Counts by Visit Time
- 16.2.6.5.2 Listing of CD3+CD19+ T cells Before and After Treatment with Rimiducid in Subjects with Graft-versus-Host Disease
- 16.2.6.6 Specific Disease Indications Status
- 16.2.6.7 Neutrophil Engraftment and Platelet Engraftment as Determined by Neutrophil Counts and Platelet Counts
- 16.2.6.8 Graft Failures
- 16.2.6.9 Types and Severity of Infectious Complications by Time
- 16.2.6.10 Engraftment
- 16.2.6.11 Hospitalizations
- 16.2.6.12 Listing of Hospitalizations Following AP1903 (Rimiducid) Administration
- 16.2.7.1 All Recorded Adverse Events
- 16.2.7.2.1 Serious Adverse Events
- 16.2.7.2.2 Serious Adverse Events in Subjects Not Infused with BPX-501
- 16.2.7.2.3 Adverse Events in Subjects Treated with BPX-501 During Phase I Dose Escalation, Including Dose-Limiting Toxicities
- 16.2.7.3.1 Adverse Events Leading to Interruption or Discontinuation of Therapy or Permanent Discontinuation of Study Medication (BPX-501/AP1903)
- 16.2.7.3.2 Adverse Events Related to BPX-501
- 16.2.7.3.3.1 Adverse Events Occurring After Administration of AP1903 (Rimiducid)

- 16.2.7.3.3.2 Adverse Events Related to AP1903 (Rimiducid)
- 16.2.7.3.4 Adverse Events Grades 3-5
- 16.2.7.3.5 Neurotoxicity Adverse Events
- 16.2.7.4 Adverse Events Leading to Death
- 16.2.7.5 Deaths
- 16.2.7.6 Infection Adverse Events
- 16.2.7.7 Infection Adverse Events Requiring Antiviral, Antibacterial or Antifungal Concomitant Medication Use Within 7 Days
- 16.2.8.1.1 Subject Hematology Results and NCI CTCAE
- 16.2.8.1.2 Subject Abnormal Hematology Results and NCI CTCAE Grades
- 16.2.8.2.1 Subject Chemistry Results and NCI CTCAE Grades
- 16.2.8.2.2 Subject Abnormal Chemistry Results and NCI CTCAE Severity Grades
- 16.2.8.3 Vital Signs
- 16.2.8.4 Physical Examination, Karnofsky/Lansky Performance Status and WHO Score
- 16.2.8.5 ECG Results and Findings

References

HoV.T., Soiffer R.J. The history and future of T-cell depletion as graft-versus-host disease prophylaxis for allogeneic hematopoietic stem cell transplantation. *Blood*. 2001; 98:3192-3204
